# 7. Study Procedures & Data Collection

# **Baseline Imaging: CT**

Each patient will have a diagnostic CT within 180 days prior to enrollment (as part of the standard of care) to define the pathologic conditions necessary to be enrolled, and be untreated for the IPN or lung cancer for which the patient is being evaluated. These prior scans must be immediately available to the investigators for review. Outside CT scans found to be of good quality will be acceptable if they are available in native (uncompressed) DICOM format.

# Imaging Protocol: F-FSPG (Figure 1)

[figure not shown]
Each patient will undergo an SOC whole-body (vertex to mid thighs) F-FDG PET/CT scan within 60 working days of an F-FSPG PET/CT scan for these first 60 enrollees, with no intervening cancer treatment of the target lesion (limited biopsies or resections are allowed). A minimum of 12 hours must lapse between SOC (F-FDG) and F-FSPG PET/CT scans. Standard of care procedures performed prior to consent but within the protocol defined windows for each

assessment can be used for study purposes. All research only procedures must be performed after the consent date.

Eight (8) subjects with either indeterminate nodule(s) or thought or known to have newly diagnosed lung cancer, will receive an F-FSPG PET scan (emission only), acquired dynamically after injection over the nodule/mass of interest for 60 minutes, in order to characterize the time activity curves of F-FSPG. These 8 subjects will then have a short break (bathroom, stand up) and then receive a PET/CT scan from the vertex to the mid-thighs. This final body PET/CT covers the same anatomic range as the SOC F-FDG PET/CT, and will be compared closely to the F-FDG PET/CT to determine if there is added value of the F-FSPG PET/CT. Once the dynamic PET/CT scans with F-FSPG in the initial 8 subjects are obtained, the remainder of subjects will have a scanning protocol from vertex to mid-thighs about 60 minutes after F-FSPG injection, similar to the protocol for standard of care F-FDG PET/CT.

The third year will be used, if needed, to obtain at least two years of CT follow-up for patients with IPNs who chose serial follow-up CT scans over a tissue diagnosis (two years is required by Fleischner Society Guidelines to prove stability/benignity for solid nodules), though over 90% of malignant IPNs will demonstrate growth within one year by CT.

Figure 1: Flow Schema of Imaging:

\*Optional tissues collection noted in Figure 1 are part of separately enrolled study and not called for on this protocol.

It is possible that we will complete enrollment of sufficient patient numbers prior to the end of year 1, in which case we will continue the clinical follow-up period for the remainder of the proposed investigational period until the end of the proposed funding or until (if sooner) we achieve clear statistical advantage of F-FSPG over F-FDG PET/CT for the diagnosis of IPNs and/or staging of lung cancer. If statistical superiority of F-FSPG PET/CT is established, we will initiate a larger trial (additional 40 subjects) for the use of F-FSPG PET/CT in the diagnosis if IPNs (Specific Aim 1) and/or evaluation of lung cancer (Specific Aims 2 and 3) (*see* Go/No-Go criteria in Study Design).

At Vanderbilt University Medical Center, the human PET scanners are integrated PET-CT systems. Therefore, a whole body transmission CT scan without contrast is performed on all patients who undergo a PET scan. The transmission CT scan is used to correct the PET images for attenuation and provide CT images for anatomical mapping. The F-FSPG will be prepared by the Vanderbilt University Medical Center Radiochemistry Core Laboratory under IND 124202 ([name], PI). For consistency, patients will fast at least four (4) hours and the blood glucose concentration ("finger-stick" in the PET area) will be determined prior to injection of all radiopharmaceuticals.

Analysis of F-FDG and F-FSPG PET/CT images will be performed independently by at least 2 physicians at VUMC who are experienced in PET/CT interpretation with a third physician used for consensus if there is a disagreement as to interpretation. The images will be interpreted with US FDA software on VUMC's GE Healthcare AW 2 and/or Xeleris 3 workstations.

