#### 5. Enrollment/Randomization

We propose a three (3) year funded prospective cohort with consecutive subject enrollment throughout each year. We will enroll subjects referred to the Oncology, Thoracic Surgery or Pulmonary Medicine Services at Vanderbilt University Medical Center and Tennessee Valley Healthcare System Nashville. We will allow a 2-year follow-up of all subjects to document stability by CT for IPNs that do not have a tissue diagnosis (stability on CT for two years of an IPN or mass is accepted presumptive evidence of benignity). Follow-up will be from the day of the baseline CT, and may be extended later if needed. At VUMC, we see about 750 patients with newly diagnosed IPNs annually, and about 400 patients with newly diagnosed lung cancer. Accordingly, given the high prevalence of granulomatous IPNs in our geographic region, we are well suited to perform the work we have described.

We will perform an analysis to correlate the F-FSPG PET/CT findings with F-FDG PET/CT and the surgical pathology results for the patients who have tissue correlation. Each subject will receive the "standard-of-care" F-FDG PET/CT as indicated for patients at high risk for lung cancer who have an IPN or lung mass meeting our size criteria, and will also receive the investigational F-FSPG PET/CT, with no intervening treatment of the target lesion(s). After enrolling 30 subjects, we will close enrollment but continue the study for data collection and analysis until the funding period ends and/or sufficient follow-up for diagnosis (up to 2 years) has occurred, and report our results in the peer-reviewed literature.

Should we achieve clear statistical superiority of F-FSPG PET/CT over F-FDG PET/CT before that time, we will pursue a larger trial to offer improved benefit of our patients for the diagnosis of IPNs and/or staging of lung cancer (*see* Go/No-Go criteria in Study Design). While 2 years' stability in nodule size is the "gold standard" for CT, well over 90% of cancers demonstrate growth on CT within one year. We will also perform the research outlined in Specific Aim 3 on tissue specimens obtained from our subjects in Specific Aims 1 and 2. If we find significant added value from the use of F-FSPG in either IPNs or lung cancer, we will propose further investigations.

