Final diagnosis will be based on tissue biopsy (surgical or *via* a high-quality core biopsy) or negative (no growth) two-year follow-up with CT. We will assign patients with IPNs into the

"benign" category if their IPNs remain stable for two or more years, decrease in size, or resolve during CT follow-up, performed in accordance with Fleischner Society guidelines.

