# 13. Follow-up and Record Retention

Study results will be retained in the research record for at least six years after the study is completed. At that time, the research information not already in the patient's medical record will be stored in a locked file cabinet in the Vanderbilt Clinical Trials office. Any research information in the medical record will be kept indefinitely.

Following closure of the study, each participating center will maintain a copy of all site study records in a safe and secure location. The Coordinating Center will inform the investigator at each site at such time that the records may be destroyed.

Study Procedure Calendar (2-year follow-up by CT only needed for subjects without a definitive diagnosis of the nodule or mass by biopsy)

	Year 0: Study Initiation	Year 1	Year 2
Initial Visit	x		
Consent	х		
Finger-stick Glucose (in PET/CT lab)	x		
Blood draw (for pregancy test for female subjects of childbearing potential only)	x		
Chest CT Review	SOC	SOC	SOC
 F-FSPG PET/CT	х		
 F-FDG PET/CT	SOC		
Adverse Event Follow- up	Performed day after  F-FSPG scan as described		

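### If enrollment finishes within year 1, Section 7 lets follow-up end at an undefined statistical advantage of FSPG, in conflict with the two-year CT outcome required elsewhere for stable, unbiopsied nodules

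*Combined protocol and SAP*

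**What the plan says.** The early-end rule is in Section 7, Imaging Protocol. If enrollment completes before the end of year 1, follow-up continues "until the end of the proposed funding or until (if sooner) we achieve clear statistical advantage of" FSPG over FDG "for the diagnosis of IPNs and/or staging of lung cancer". The next sentence says that, if superiority is established, a larger trial with 40 additional subjects will start, and it refers to the Go/No-Go criteria.

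Other parts of the plan set a different end to follow-up:

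- Section 5: "We will allow a 2-year follow-up of all subjects to document stability by CT for IPNs that do not have a tissue diagnosis". The clock is stated: "Follow-up will be from the day of the baseline CT". After 30 subjects, enrollment closes and data collection goes on until funding ends and/or "sufficient follow-up for diagnosis (up to 2 years) has occurred".
- Section 5, final diagnosis: without tissue, nodules are benign if they "remain stable for two or more years, decrease in size, or resolve during CT follow-up".
- Section 7, a little earlier: "The third year will be used, if needed, to obtain at least two years of CT follow-up for patients with IPNs".
- Study Procedure Calendar (Section 13): "2-year follow-up by CT only needed for subjects without a definitive diagnosis of the nodule or mass by biopsy".

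Section 5 also considers superiority appearing early. Its only stated consequence there is pursuit of a larger trial. Inclusion criterion 6 (Section 4) has subjects agree to indicated biopsy or 24 months of follow-up, as needed.

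**The concern.** The length of follow-up decides which benign nodules have a reference diagnosis, and so who enters the specificity denominator. Specificity is the quantity that Section 11 sizes the study on. A rule that ends follow-up when the comparison looks favourable makes that denominator depend on the result.

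Three features of the clause matter.

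- **The trigger is undefined.** The Go/No-Go criteria that the passage points to are assessed at the end of enrollment and data analysis. For Aim 1 they are point thresholds (equal sensitivity, specificity of at least 50%), not a test of superiority.
- **The scope is wide.** Because of the 'and/or', an advantage in staging alone would meet it and end the CT follow-up that specificity needs.
- **Its wording suggests more than one look.** The only error rate in the plan, two-sided 5% in Section 11, belongs to a single fixed-size McNemar test.

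**Working it through.** **1. The plan's own test.** Section 11 gives discordant proportions 0.6 and 0.2, two-sided 5% and 80% power. The usual McNemar formula gives

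n = (1.960 × √0.8 + 0.842 × √(0.8 − 0.4²))² / 0.4² = 36.8, so 37 benign, and 37/0.6 = 61.7, so 62 in total.

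Both match the plan. They describe one analysis at a fixed size.

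**2. Which cohort the clause concerns.** Section 5 closes enrollment at 30, Section 7 adds 40, and Section 11 speaks of 70 in total. Since 30 + 40 = 70, the natural reading is 30 subjects. At the plan's 40% cancer prevalence that is 0.6 × 30 = 18 benign. Sections 7 and 11 also mention 60 or 62, so 37 benign applies only if that cohort is meant.

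**3. Timing.** The qualifying CT is at most 180 days before enrollment (Section 7, Baseline Imaging), and 180/30.44 = 5.9 months. Taking it as the baseline CT:

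- longest possible CT follow-up 12 months after first enrollment: 12 + 5.9 = 17.9 months;
- earliest two-year outcome: 24 − 5.9 = 18.1 months after first enrollment;
- latest two-year date if enrollment ends by month 12: at most 12 + 24 = 36 months, within the three-year funding if year 1 starts at first enrollment.

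So between months 12 and 18 no stable, unbiopsied nodule can have reached the two-year outcome on this clock. Section 4 admits lesions with less than two years of prior stability, so crediting older scans would shorten the wait.

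**4. Repeated looks (illustration).** The documents give no schedule. Assumptions: both tracers equally specific; discordance 0.3, 0.48 or 0.6; 30% or 50% of benign outcomes known at month 12, rising linearly to all at month 36; 3, 5 or 9 looks, each at unadjusted two-sided p ≤ 0.05. The table gives the chance of a false advantage for FSPG (nominal 2.5%).

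| Benign | Version | One test at the end | 3 to 9 looks |
|---|---|---|---|
| 18 | asymptotic | 2.1-2.5% | 3.8-7.4% |
| 18 | exact | 0.5-1.2% | 0.6-2.7% |
| 37 | asymptotic | 2.1-2.7% | 4.6-7.5% |
| 37 | exact | 1.2-1.5% | 1.7-4.3% |

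The linear rise is a simplification, since step 3 allows no two-year outcome before month 18.

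**5. Unequal early verification (illustration).** Suppose a fraction a of FDG-positive and b of FDG-negative benign nodules are resolved at a single early look. Both tracers are 40% specific with independent reads. Each discordant cell is 0.6 × 0.4 = 0.24, so the verified cells are 0.24a (favouring FSPG) and 0.24b (favouring FDG). Observed FDG specificity is 0.4b/(0.4b + 0.6a). For 18 benign:

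| a / b | Observed FDG specificity | False FSPG advantage, asymptotic | Exact |
|---|---|---|---|
| 25% / 50% | 57% | 0.3% | 0.0% |
| 50% / 50% | 40% | 2.4% | 0.3% |
| 50% / 25% | 25% | 6.4% | 0.7% |
| 60% / 10% | 10% | 17.6% | 2.6% |

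Only 18 × 0.24 × (a + b) = 3.0 to 4.3 discordant pairs are expected in these cases. The asymptotic test already rejects at 4 of 4 (z = 4/√4 = 2), where the exact two-sided p is 2 × 0.5⁴ = 0.125. In the 50/25 and 60/10 cases, 18 × (0.6a + 0.4b) = 7.2 benign nodules are resolved and about 11 are not.

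**The case against.** The best case for the plan is that this is one conditional sentence in a pilot, and that the surrounding text points the other way. Subjects agree at entry to 24 months of follow-up as needed, Section 5 says follow-up may be extended, and Section 5 attaches only a larger trial to early superiority. Standard-of-care CTs would probably continue. At about 18 benign subjects the exact test shows essentially no inflation. All of that stands, and it limits the size of the point. It does not remove the conflict: Section 7 states a different end to follow-up, and nothing obliges the study to collect CTs after that end.

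The plan also notes that over 90% of cancers show growth within a year. That is reassuring about missed cancers (at most about 0.1 × 12 = 1.2 among 12 cancers in 30 subjects), but Section 5 still requires two years for a stable nodule.

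A reader might infer three stronger things that the documents do not support.

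- **That the plan intends to stop early or to count unresolved nodules as benign.** Section 7 permits the stop, but nothing shows intent, and the Section 5 definition would leave such nodules unresolved rather than relabel them.
- **That an early stop must favour FSPG.** FDG is the clinical scan and FSPG does not direct care, so FDG-positive nodules may be resolved sooner. No verification rates are given, though, and equal or reversed rates give no bias or the opposite one.
- **That error rates are grossly inflated.** Larger figures arise with 37 benign subjects and strongly unequal verification (60/10: 44.5% asymptotic, 25.2% exact). That combines a cohort the clause probably does not concern with an assumed pattern implying 10% observed FDG specificity, against the plan's 40%.

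**Conclusion.** The rule is wrong as written and should be fixed. It contradicts the two-year outcome in Sections 5, 7 and 13 and makes the end of follow-up depend on an undefined favourable result. This conclusion rests on the text and needs no simulation.

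The reach is conditional: it applies only if enrollment completes within year 1. On the baseline-CT clock, a stop before about month 18 would base specificity on biopsied, shrinking or resolved nodules only. For the 30-subject cohort, the error from repeated looks runs from essentially none (exact, 0.6-2.7%) to moderate (asymptotic, 3.8-7.4%) against 2.5%, under assumed look schedules. Verification bias is possible in either direction and cannot be sized from the documents.

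**What to change.** In Section 7, delete the second limb of the sentence, from the 'if sooner' alternative to the mention of staging. State instead, in line with Section 5, that for the cohort enrolled in year 1 the reference outcome is collected until each subject has a tissue diagnosis, has a CT outcome meeting the Section 5 definition, has completed the two-year CT window, has withdrawn or has been lost, or until the funded period ends.

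In Section 11, run the McNemar specificity comparison once at that cut-off and name the version; exact is preferable at about 18 benign. Report subjects still unresolved by FDG result, with a sensitivity analysis classing them all as benign and then all as malignant.

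The expansion trigger is the sponsor's design decision, but its wordings need reconciling: superiority in Sections 5 and 7, point thresholds under Go/No-Go, and a trend under Data Analysis. Any 40 added subjects should be followed to the same Section 5 outcome under their own funding period, not capped by the first.

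Deleting the clause and specifying the single analysis adds no subjects or scans. The cost is a later readout, using chest CTs that the calendar already lists as standard of care.

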#### Radiotracer Production

F-FSPG is obtained by radiolabeling of the protected precursor di-*tert*-butyl (2*S*,4*S*)-2-(3-((naphthalen-2-ylsulfonyl)oxy)propyl)-4-(tritylamino)pentane-dioate) (PI-021) with [F]fluoride. After acidic deprotection, the tracer is purified over cartridges and finally formulated for i.v. injection by passing the solution through a 0.22-Im sterile filter. It has a half-life of 109.7 minutes. The synthesis is performed within an automated synthesis module in a lead-shielded hot cell. The production methods, sterile filtration, and formulation are all carried out under Vanderbilt-held IND 124202, and allow for the production of a sterile and pyrogen-free solution ready for injection.

#### Clinical Data Analysis

The research PET/CT studies will be interpreted independently by two experienced nuclear medicine (NM) physicians blinded to each other's interpretation. These NM physicians will render "un-blinded" interpretations with access to conventional imaging studies and all other

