# THO 1524: [F]FSPG PET Protocol

relevant information available in the patients' medical records. The final PET/CT interpretations (F-FSPG; F-FDG PET/CT, clinical CTs and other relevant clinical imaging available for comparison) will then be compared to determine the impact of F-FSPG PET/CT on the final diagnosis, and specifically to determine if the F-FSPG PET/CT would have changed the diagnosis and/or stage of disease compared to the clinical SOC CT and/or F-FDG PET/CT. These results will be reported to the biostatistician who will compile the data for estimation for analysis (*see* Statistical Consideration Section).

At this time, the investigational data will not be used to direct care (e.g. influence treatment decisions) until we have sufficient knowledge of the usefulness of the data in this regard compared to standard of care procedures.

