# **Data Analysis**

As part of our "go/no go" analysis as initial proof of principle, we plan to enroll 30 subjects initially with IPNs or newly discovered lung masses, to determine if this initial enrollment will demonstrate a trend toward significance in accuracy for diagnosis of IPNs or lung masses. This will be an initial, "proof of principle" investigation. If not, we will consider other imaging probes. However, if we do see a trend of significance, we plan on 70 subjects to complete a study.

We will not know at time of enrollment if the subject has a benign or malignant IPN or mass. Historically, we have a 40% prevalence of cancer in our referral base, which, heretofore, is not a "screened" population. Thus, with 70 subjects completing a study, we expect that, after tissue confirmation or adequate clinical follow-up to establish benignity is established, to have about 42 subjects with benign nodules and 28 with cancer. The analysis of Specific Aim 1 will focus on the F-FSPG PET/CT's ability to discriminate up-front benign from malignant lung nodules/masses in all subjects. Analysis of Specific Aim 2 will then focus on analysis of known/confirmed lung cancers. Specific Aim 3 analysis will correlate the biomarker findings as described elsewhere in the Project Narrative with the findings of Specific Aims 1 and 2.

Sensitivity, specificity, overall accuracy and ROC curves will be generated and compared for both F-FDG and F-FSPG tests. Wilcoxon rank-sum or Kruskal-Wallis tests will be applied for the group comparisons of immunohistochemical staining (CD44 and  $x_c^-$  expression levels, Specific Aim 3) and the biodistribution characteristics of F-FDG and F-FSPG tests (Specific Aims 1 & 2). The demographic information such as age, smoking status/pack-year history will be tabulated. Descriptive statistics, including means, standard deviations, and ranges for continuous parameters (uptake expressed in SUVmax, SUVmean, SUVpeak) normalized to lean body mass and body weight, and ratios of these uptake values to cardiac blood pool and normal lung. as well as percentages and frequencies for categorical parameters, will be presented.

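### No masked read is specified for the FSPG-versus-FDG accuracy comparisons: the only PET read described in detail is un-blinded, and the plan does not say which read feeds the analysis

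*Combined protocol and SAP*

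**What the plan says.** Two places in Section 7 describe how the PET scans are read.

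- **Imaging Protocol.** Images from both tracers are analysed "independently by at least 2 physicians at VUMC who are experienced in PET/CT interpretation with a third physician used for consensus" when they disagree. Masking to the other tracer, clinical data or final diagnosis is not mentioned.
- **Clinical Data Analysis.** The research scans go to two nuclear medicine physicians who do not see each other's reading. Then: "These NM physicians will render 'un-blinded' interpretations with access to conventional imaging studies and all other" relevant information in the medical record. The final interpretations, with "F-FDG PET/CT, clinical CTs and other relevant clinical imaging available for comparison", are compared to see whether FSPG would have changed diagnosis or stage. "These results will be reported to the biostatistician who will compile the data for estimation for analysis", with a pointer to the statistical section.

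Section 11 makes accuracy against FDG the primary endpoint twice, for benign/malignant discrimination and for staging. Data Analysis says "Sensitivity, specificity, overall accuracy and ROC curves will be generated and compared for both" tracers, but does not name the read. Go criterion A asks for sensitivity equal to FDG and FSPG specificity of at least 50%.

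Other relevant text:
- For the eight dynamic-scan subjects, the FSPG body scan covers the same range as the FDG scan "and will be compared closely to the" FDG scan (Imaging Protocol).
- Between the two scans, "limited biopsies or resections are allowed" (Imaging Protocol).
- Newly diagnosed lung cancers are eligible (Section 4.A).
- The immunohistochemistry pathologist is fully blinded to patient and imaging information (Pathology Methods).

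**The concern.** Both primary endpoints compare two readings of the same patient. That comparison is clean only if each tracer's call is made without the other's result and without the reference diagnosis. The visible text does not secure this for the accuracy read, although it does secure it for the pathologist in Aim 3.

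The bias could run in several directions:
- If clinical context corrects FSPG calls more often than FDG calls, FSPG looks better than it is.
- If the FSPG call follows a visible FDG result, a real gain is diluted.
- If context corrects both equally, the paired specificity test is not biased, but both specificities are inflated. The Go bar is an absolute 50%, so it becomes easier to pass even then.

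At stake is whether a Go or No-Go, which decides on further trials, reflects the tracer or the reading conditions.

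**Working it through.** **1. Which read feeds the analysis?** The un-blinded read is the only one whose results are expressly sent to the biostatistician, but its stated purpose is impact on diagnosis and stage. The consensus read covers both tracers but is silent on masking. Data Analysis names neither. The text therefore leaves the accuracy read unspecified, and neither candidate is masked.

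**2. What could be in view?**
- *The other tracer.* FDG is listed among the material available for comparison, and as standard of care it would ordinarily be in the record.
- *Tissue.* Possible for known cancers and after biopsies or resections between scans.
- *Benign status.* Much less likely. Aim 1 concerns undetermined lesions, the plan says "We will not know at time of enrollment if the subject has a benign or malignant IPN or mass", and a benign label may need two-year CT (Section 5). The timing of the reads is not given.

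On the benign side the main exposure is therefore the other tracer and clinical context.

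**3. The plan's own figure.** Inputs from Sample Size and Study Power: specificity 40% against 80%, discordant proportions 0.6 and 0.2, two-sided 5%, power 80%. With d = 0.6 − 0.2 = 0.4 and s = 0.6 + 0.2 = 0.8:

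n = [1.96·√s + 0.842·√(s − d²)]² / d² = (1.753 + 0.673)² / 0.16 = 36.8, so 37. Then 37/0.6 = 61.7, so 62. Both reproduce.

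**4. Leverage on the Go bar (pilot size).** Benign 30 × 0.6 = 18; cancers 30 × 0.4 = 12 (prevalence from Data Analysis). One re-called benign lesion moves specificity by 1/18 = 5.6 points. Assume FSPG is truly 40% specific and un-blinded reading corrects a fraction f of false positives, so apparent specificity is 0.4 + 0.6f. The documents give no value for f. The bar is met when X ≥ 9, X ~ Binomial(18, 0.4 + 0.6f).

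For equal sensitivity, read here as FSPG true positives at least equal to FDG true positives in 12 cancers, with both tracers at 0.92 and independent, the probability is 65.9%. The last column multiplies by it.

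| f | Apparent specificity | Specificity ≥ 50% | With equal sensitivity |
|---|---|---|---|
| 0 | 0.40 | 26.3% | 17.4% |
| 1/12 | 0.45 | 42.2% | 27.8% |
| 1/6 | 0.50 | 59.3% | 39.1% |

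These figures are the same whether or not FDG calls are corrected too.

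**5. Dilution if FSPG copies FDG (full-study size, 37 benign).** If FSPG follows FDG on a fraction g of discordant calls, both discordant proportions are multiplied by (1 − g). Power = Φ{[d√n − 1.96√s] / √(s − d²)}. At g = 0 on the plan's inputs: (2.433 − 1.753)/0.8 = 0.85, giving 80.2%.

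| g | Plan's 0.6/0.2 | Independent errors, 0.48/0.08 |
|---|---|---|
| 0 | 80.2% | 93.7% |
| 0.1 | 75.3% | 90.4% |
| 0.2 | 69.7% | 86.0% |
| 0.3 | 63.3% | 80.2% |

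The second column uses 0.8 × 0.6 = 0.48 and 0.2 × 0.4 = 0.08. The plan's 0.6/0.2 implies that no benign lesion is positive on both tracers (0.6 + 0.2 + 0.2 negative on both = 1), so the size of the loss depends heavily on that assumption.

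**The case against.** A fair defence has four parts.

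- *The un-blinded read is an impact read.* Its declared purpose suits full clinical context, and the results sent to the biostatistician may be only that comparison. It also refers to research scans, so it may not govern the FDG read. This stands. A reader might infer that the accuracy data are known to come from the un-blinded read; the documents do not show that. What they show is that no masked read is named for accuracy.
- *Readers will mostly not know the answer.* This stands in large part on the benign side, which drives specificity. A reader might infer that the final diagnosis is generally open to the PET readers; the text on undiagnosed lesions and two-year CT does not support that. Nor is it clear whether cancers already known at entry count in the Aim 1 sensitivity test. But masking to the other tracer matters even when no tissue result exists.
- *Other safeguards exist.* Two independent readers, a consensus step, SUV measures and ROC curves reduce dependence on one reader's judgement. None of them masks the reader, and no SUV cut-off for a positive scan is stated.
- *The figures are hypothetical.* True. Every correction or copying rate is assumed, the benign count could fall below 18 because known cancers are eligible, and the power figures apply to the full study and not to the 30-subject pilot.

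**Conclusion.** The point holds as a gap in specification that permits bias. As written, the FSPG-versus-FDG comparisons for diagnosis and staging may rest on calls made with the other tracer, and for some subjects tissue results, in view. The size and direction of any bias cannot be derived from the documents, so a claim that the plan favours FSPG would go too far.

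The illustrations show only that small shifts matter. With 18 benign lesions and a true specificity of 40%, correcting 1 in 12 to 1 in 6 false positives moves the chance of meeting the specificity bar from 26% to 42–59%, and of meeting both parts of the criterion from 17% to 28–39%. In the other direction, copying FDG on 10–30% of discordant calls lowers full-study power from 80% to 75–63% under the plan's discordance, or from 94% to 90–80% under independent errors.

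This is a proof-of-principle study whose scans do not direct care, and a Go leads to further trials only. The change is best seen as a cheap improvement.

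**What to change.** In Section 7 (Imaging Protocol and Clinical Data Analysis), state that for the accuracy comparisons in Section 11:

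1. The planned readers and the consensus reader first record and lock a call for each tracer, masked to the other tracer's PET, tissue results and follow-up.
2. The baseline diagnostic CT, which defines the lesion, is equally available for both tracers.
3. The two tracers' cases are read in separate, shuffled sessions, since the same readers handle both.

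In Section 11, state that these locked calls feed the McNemar, non-inferiority, staging and Go/No-Go analyses and any reader-based ROC curve, with the SUV measures already listed reported alongside. Keep the un-blinded read as a second step, used only to judge whether FSPG would have changed diagnosis or stage.

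Cost: protocol wording, one more reading pass per tracer on 30 to 70 cases by readers already planned, and some scheduling. No extra patients or scans are needed. The accuracy estimates may come out less favourable than with full clinical context.
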